B. Outcome: This research study seeks a better understanding of patients with lumbar failed back surgery syndrome and how they compare to patients with chronic low back pain (without a history of surgery) and healthy controls. Gaining a foundational understanding about the influence of CNS pain amplification in FBSS and whether these testing paradigms may be able to tease apart two possible subsets of centralized pain in FBSS: “top-down” vs “bottom-up” wherein the latter would represent a FBSS cohort that may be amenable to differing peripheral interventions compared to the former. Ultimately, the goal of the proposed research and future studies is to gain data and information that will allow for “personalized medicine and analgesia” for optimal and individualized treatment of chronic lumbar spine pain (including FBSS) and risk stratification with appropriate directed therapies for perioperative lumbar spine patients. The knowledge to be gained through these studies will also provide important objective information on the biochemistry and function of neurochemical systems in the human which is not obtainable by other means. These outcomes are central to the study of pain mechanisms and their response to treatment. There is no “success” or “failure” of this study as this is observational and seeking to generate data for further investigations. The end point of the study will be when all surgical patients have finished their 6 month follow up visit.

C. Study results to participants: At the conclusion of the study, when results are published in journals, study participants will be contacted to determine if they would like copies of the published results.

D. Publication Plan: At least one publication will result from the proposed research.

VI. Bibliography / References / Literature Cited: See below.

1. Medicine. Io. Relieving Pain in America: A Blueprint for Transforming Prevention, Care, Education, and Research. . Washington, DC: The National Academies Press. ; 2011.
2. Katz JN. Lumbar disc disorders and low-back pain: socioeconomic factors and consequences. *The Journal of bone and joint surgery American volume*. 2006;88 Suppl 2:21-24.

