Overall Study Design. For Aims 1 and 2, a prospective, observational study will recruit 100 men and women with chronic low back pain (+/- leg pain) who are scheduled to undergo lumbar spine surgery at the University of Kansas Medical Center (KUMC). 50 will participate in phenotypic characterization and 50 will participate in phenotypic characterization and quantitative sensory testing (QST) procedures. After screening, informed consent, and enrollment into the study, all subjects will undergo an evaluation which includes a comprehensive battery of questionnaires for patient phenotyping that will assess symptoms including pain, physical function, depression, anxiety, and catastrophizing symptoms. QST parameters will only be performed on half of the cohort of lumbar spine surgery patients. Patient phenotyping and QST procedures will take place in one visit pre-operatively. At two weeks, one month, three months, & six months post-surgery, we will administer one questionnaire to determine analgesic response to surgery. This will establish longitudinally-designated post-surgical analgesic outcome groups (see Statistical Analysis section for definitions). Instead of just a three month time point that is often used in analgesic trials, a six month time point was chosen to give adequate time for recovery and response to surgery. Phenotyping and QST will also be done in a cross-sectional manner on 50 age and sex-matched healthy controls and 50 age and sex-matched patients with an established diagnosis of FBSS (established-FBSS) to compare to the longitudinally-designated post-surgical analgesic outcome groups. For Aim 3, 30 men and women with chronic low back pain (+/- leg pain) who are scheduled to have lumbar spine surgery at KUMC will undergo pre-operative functional, structural, and chemical neuroimaging studies. 15 age and sex-matched healthy controls and 15 age and sex-matched established-FBSS patients will also undergo the same neuroimaging studies to compare to the longitudinally-designated post-surgical analgesic outcome groups. Patients for Aim 3 will be recruited from both the prospective and cross-sectional cohorts enrolled for Aims 1 and 2. The goal of the studies in Aim 3 are to investigate whether pre-operative functional, structural, and chemical neuroimaging findings known to be associated with centralized pain and indicative of CNS amplification are associated with the centralized pain phenotype and possibly predictive of failure to achieve pain relief after lumbar spine surgery. We acknowledge that these studies are exploratory and may be underpowered but feel that they will at a minimum provide critical preliminary data for future studies.

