
C. Sample size, statistical methods, and power calculation

Aim 1 Analyses: To demonstrate that common patient characteristics consistent with a centralized pain phenotype are associated with a patient's failure to derive benefit from lumbar spine surgery. **Analysis**

1a: Analgesic outcomes (AOC) for patients in the prospective cohort will be defined as "AOC-success" or "AOC-failure" for the purposes of further analyses. AOC-success is defined as those who demonstrate a 50% reduction in pain scores from baseline to 6 months, which would be a response more commensurate with the invasiveness of the intervention of spine surgery than a minimal clinically important difference score (MCID). FMness as measured by the 2011 FM Survey Criteria score⁶⁶ is the primary measure of interest and will be split by median score (and defined as FM-high and FM-low). Differences in surgical failure proportions (determined by pain score change as described above at 6-months) between the FM-high (n=50) and FM-low (n=50) groups will be tested using a two-sided chi-squared statistic at $\alpha=.05$. In addition to FMness, differences between AOC-success and AOC-failure groups for each of the constructs contained under the subheading "Comprehensive Phenotyping Battery" will be examined using appropriate parametric or non-parametric analyses. Furthermore, we wish to explore how multiple patient characteristics vary across these cohorts. A stepwise logistic regression model will then be fit to evaluate multivariate relationships. The analyses conducted in this aim will provide the candidate an opportunity to learn multivariate data analysis with advanced regression modeling as well as more familiarity with patient reported outcome measures. **Analysis 1b:**

Phenotypic differences between the AOC-failure group and the established-FBSS group will be examined using appropriate parametric or non-parametric tests to see if the longitudinally designated AOC-failure cohort is phenotypically similar in nature to the cross-sectional established-FBSS patients. We hypothesize that AOC-failure patients will appear similar to established-FBSS patients. The same comparisons will be explored for the longitudinally designated AOC-success group compared to the cross-sectional healthy controls group.

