Sample size for Study Procedures in Aims 1 and 2: We anticipate screening approximately 60 pre-operative lumbar spine surgery patients per year for possible enrollment into the study. Assuming a 50-60% recruitment rate, we estimate approximately 30-35 lumbar spine surgery patients enrolled per year during Years 1-4 of the award. This leads to an estimated total sample size of 100 lumbar spine surgery patients. We will also aim to recruit and enroll equal distributions of established-FBSS patients (n=50) and healthy controls (n=50). For the assumed effect size (population of 0.10 vs 0.50) and sample sizes (50 and 50 based on 2011 FM Survey Criteria score median split) and $\alpha=.05$ (two-sided) the power is 0.99. Several different assumptions were also explored. For example, if the assumed effect size is (population of 0.15 vs 0.45) or (population of 0.17 vs 0.43), then the respective power calculations are 92% and 82%, both which are adequate for significance purposes (e.g., >80%). The larger sample size will also be important for exploring multivariate models and potential subgroup analyses. The inclusion of healthy controls and established-FBSS patients will ensure adequate matching of gender and age to the patient cohorts for analyses.

Sample size for Study Procedures in Aim 3: We aim to recruit 30 lumbar spine surgery patients, 15 healthy controls, and 15 established-FBSS patients out of the total cohort to participate in the

neuroimaging study procedures. As this study is powered for the primary hypothesis in Aim 1, issues of power are of less concern for these investigatory neuroimaging studies.

D. Subject Criteria (See Vulnerable Populations appendix, if applicable):

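### The plan has no continuous, baseline-adjusted analysis of 6-month pain beside the 50% responder split: a missed gain in precision, not an error

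*Combined protocol and SAP*

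**What the plan says.** Section II.C, Aim 1 Analyses, Analysis 1a fixes the outcome: "AOC-success is defined as those who demonstrate a 50% reduction in pain scores from baseline to 6 months". The only reason given for 50% is that it is "which would be a response more commensurate with the invasiveness of the intervention of spine surgery than a minimal clinically important difference score". Section II.B (Overall Study Design) says of the follow-up questionnaires: "This will establish longitudinally-designated post-surgical analgesic outcome groups".

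The primary test is a two-sided chi-squared comparison of failure proportions at 0.05 "between the FM-high (n=50) and FM-low (n=50) groups". The remaining analyses that use surgical outcome take the same split:

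- Success and failure groups are compared on each phenotyping construct.
- A stepwise logistic regression is fitted.
- Analysis 1b compares the success and failure groups with the cross-sectional cohorts.
- Aim 2 repeats the Aim 1 methods. The measures it calls continuous are the sensory-testing scores, not 6-month pain.
- Analysis 3b relates imaging to success or failure status.

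The finer data are collected. Section II.E lists the Brief Pain Inventory on 0-10 scales, and the Study Schedule shows it, with surgical-site pain severity, at baseline and at 6 months for the surgical cohort.

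**The concern.** A responder split treats a patient with a 49% reduction like one who got worse, and a patient at 51% like one who is pain-free. Baseline pain enters only as the denominator of the percentage, so two patients with the same 6-month score can be classed differently because they started at different levels. The sentence defending 50% answers the question of which cut-off to use. It does not say why pain should be analysed only through a cut-off.

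The study is meant to supply preliminary data for a larger grant application. At the 30% average failure rate implied by the plan, 100 patients give about 30 failures (100 x 0.30). An association could be estimated imprecisely, or missed, although the collected scores would show it more clearly.

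**Working it through.** **Inputs from Section II.C.** Two groups of 50 by median split of the FM score, two-sided alpha 0.05, and three pairs of failure rates: 0.10 vs 0.50, 0.15 vs 0.45 and 0.17 vs 0.43. Each pair averages 0.30. The cohort size is given as "This leads to an estimated total sample size of 100 lumbar spine surgery patients", with no stated allowance for missing 6-month data.

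**Step 1: the plan's own power.** Chi-squared test, pooled variance under the null, no continuity correction:

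power = Φ{ [(p2 − p1) − 1.96·√(2·p̄(1−p̄)/n)] / √([p1(1−p1) + p2(1−p2)]/n) }

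For 0.17 vs 0.43 with n = 50 per group: (0.26 − 0.1796) / 0.0879 = 0.914, and Φ(0.914) = 0.820. The three scenarios give 0.996, 0.918 and 0.820, against the stated 0.99, 92% and 82%. The plan's figures reproduce.

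**Step 2: information kept by the cut.** Assume a normal outcome cut so that a proportion p fails. Relative efficiency is φ(z_p)² / [p(1−p)]. At p = 0.30, z = −0.524 and φ = 0.348, so 0.348² / 0.21 = 0.576. About 58% is kept, so 100 patients count as about 58. Over failure rates of 10% to 50% the share kept runs from 34% to 64%.

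**Step 3: change only the outcome, keeping the FM median split.** Assume normal outcomes with equal SDs and a cut that gives the stated failure rates. The group difference in SD units is d = z(p2) − z(p1), and power = Φ(d·√(n/2) − 1.96), with √(50/2) = 5.

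| Failure rates | d | Binary outcome | Continuous outcome |
|---|---|---|---|
| 0.10 vs 0.50 (plan) | 1.28 | 0.996 | >0.999 |
| 0.15 vs 0.45 (plan) | 0.91 | 0.918 | 0.995 |
| 0.17 vs 0.43 (plan) | 0.78 | 0.820 | 0.973 |
| 0.20 vs 0.40 (assumed, not in plan) | 0.59 | 0.590 | 0.837 |

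The exact t-test values in the last two rows are 0.971 and 0.830, hence about 97% and about 83%. If only 40 per group were evaluable (an assumption), 0.17 vs 0.43 gives 0.73 binary and 0.94 continuous.

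**Step 4: bounded scores and baseline adjustment.** Step 3 has no baseline variable and no floor. Two simulations used rounded 0-10 scores with baseline pain of at least 4. All their parameters are assumed.

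- SD 2.5, correlation of baseline with 6-month pain 0.1 to 0.5, and failure rates of about 0.16-0.19 vs 0.41-0.42. Power was 0.71-0.78 for chi-squared and 0.90-0.96 for the baseline-adjusted comparison.
- SD 2.5, baseline slope 0.4, FM split kept. Power was 82% vs 95% when the FM score and baseline pain are uncorrelated, and 79% vs 86% when their correlation is 0.5.

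A gain remained in every case, but its size varies with values that the documents do not supply.

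**The case against.** The aims are framed as failure to derive benefit, and a responder outcome answers that directly. The Background also reports an arthroplasty study that used failure to reach 50% improvement, so the endpoint allows comparison. The stated power is adequate for the stated effects, and a plan need not justify every supporting analysis it omits. All of this stands. It is why the 50% criterion should remain primary.

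Three stronger readings are tempting, and the documents do not support them.

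- *The power statement or the primary test is wrong.* The test is valid, and the figures reproduce for the plan's assumed rates.
- *The outcome cut costs the whole distance from 82% to over 99%.* That contrast, from a bivariate-normal model matched to 0.17 vs 0.43, also undoes the FM median split. In the same model, using the continuous FM score with the binary outcome already reaches 95%. The median split is a separate matter; the outcome cut alone is the 82% to about 97% in Step 3.
- *Baseline pain is never adjusted for.* It belongs to the phenotyping battery and could enter the stepwise logistic model. Its entry is not guaranteed, however, and the outcome there is still binary.

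Analysis 1b also needs outcome groups to compare with the other cohorts, and a regression cannot replace them.

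**Conclusion.** The point holds as a missed, inexpensive gain in precision. No continuous analysis of 6-month pain with assured baseline adjustment is planned, although the scores are collected, and the reason given for 50% does not address the omission.

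Under a normal outcome at 30% failure, the cut discards about 42% of the information (100% − 58%). At the plan's least favourable scenario it leaves power at 82% where about 97% was available. The larger practical loss, 59% against about 83%, arises only if the effect is smaller than any the plan assumes.

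The documents give no pain SD, outcome distribution or correlation between the FM score and baseline pain. Floor effects on a 0-10 scale shrink the gain, and so does a substantial FM-baseline correlation. The direction is well supported; the exact size is not.

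**What to change.** Keep the 50% responder chi-squared test as primary, and keep the success and failure groups for Analysis 1b. Add to Section II.C one pre-specified supporting analysis: a linear regression of 6-month pain on the continuous FM score, with baseline pain, age and sex as covariates. Report it in pain points per FM-score unit with a 95% confidence interval. Name the pain item and use the one that defines success, because the Study Schedule lists both surgical-site severity (worst, average) and the overall Brief Pain Inventory.

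Label any use of this model for other constructs, or for sensory testing in the 50 surgical patients who receive it, as exploratory.

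The cost is one added model and a second result scale to report, with no new data or visits. Extending the model beyond the FM score would add multiplicity across a long battery, which is why the pre-specified part should stay at one model.

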to accurately "phenotype" lumbar spine surgery patients for relevant trait and state constructs associated with centralized pain. *Hypothesis 1a: Pre-operative patient characteristics associated with a centralized pain phenotype will be associated with and potentially predict a patient's failure to derive benefit from surgery intended to treat chronic pain. Hypothesis 1b: Patients who fail to obtain pain relief from lumbar spine surgery in a longitudinal cohort will appear phenotypically similar to a cross-sectional cohort of established-FBSS patients and those who do obtain pain relief from lumbar spine surgery will appear phenotypically similar (except for back pain) to healthy controls.*

Aim 2: To confirm that altered pain processing mechanisms consistent with centralized pain are seen in patients who have failed to respond to lumbar spine surgery. In order to accomplish this aim, the candidate will learn how to perform and analyze the results of quantitative sensory testing (QST) (detecting pain thresholds, testing the integrity of descending analgesic pathways, and temporal summation). *Hypothesis 2a: Pre-operative altered pain processing mechanisms consistent with centralized pain will be associated with and potentially predict a patient's failure to derive benefit from surgery intended to treat chronic pain. Hypothesis 2b: Patients who fail to obtain pain relief from lumbar spine surgery in a longitudinal cohort will have augmented QST changes similar to a cross-sectional cohort of established-FBSS patients and those who do obtain pain relief from lumbar spine surgery will have QST changes similar to healthy controls.*

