Aim 2 Analyses: To confirm that altered pain processing mechanisms consistent with centralized pain are seen in patients who have failed to respond to lumbar spine surgery. Pain thresholds, cuff algometry, CPM, and temporal summation scores will be treated as continuous measures and normality will be assessed prior to analysis. The same analyses as those conducted for Aim 1 will be used for this aim.

Aim 3 Analyses: To investigate whether structural, functional, and chemical brain imaging provides evidence of the neurobiological signature for centralized pain in patients who fail to derive benefit from lumbar spine surgery. AFNI, BrainVoyager, LCMoel, FSL, MatLab, SPM, and Freesurfer will be used for functional MRI, structural MRI, and spectroscopy MR analyses based on the analytical methods previously described by [name] and his research colleagues.^{54,58,74,76,122,131-141} **Analysis 3a:** Pre-operative neuroimaging data for lumbar spine surgery patients will be split based on median baseline 2011 FM Survey Criteria score into two groups (FM-high and FM-low). Neuroimaging findings between these two groups will be compared and we hypothesize that lumbar spine surgery patients with higher preoperative 2011 FM Survey Criteria scores will have (1) *more hyperalgesia and decreased pain inhibition on QST and functional magnetic resonance imaging (fMRI)*, (2) *characteristic functional connectivity changes on fMRI (e.g., decreased functional connectivity to descending anti-nociceptive analgesic brain networks and increased connectivity to pro-nociceptive regions)*, (3) *increased CNS levels of glutamate in pro-nociceptive regions on proton spectroscopy*, and (4) *increases in S1/M1 gray matter volume*. **Analysis 3b:** We will perform whole brain analyses as per analysis 3a for all modalities with no *a priori* hypotheses to investigate the relationships between baseline imaging findings and post-surgical analgesic outcome status (AOC-success and AOC-failure) at six months.

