Inclusion (ALL) 
 • Able to Read and Speak English • Between 22-70 years old • Stable dose (or not on) of adjunctive pain medications for at least 2 weeks prior to QST • Able to provide informed consent 	Exclusion (ALL) 
 • Diagnosis of a medical condition that isn't minor or stable • Current litigation regarding a medical illness • Drug or alcohol abuse • Severe physical impairment • Co-morbid medical conditions that may impair physical functional status • Psychiatric condition that may impair functional status (active psychosis or suicidal ideation) • Pregnant or nursing • Liver failure, cirrhosis, hepatitis • Severe cardiovascular disease
Inclusion (ALL) QST 
 • Right-Handed • Willingness to refrain from alcohol and nicotine on the day of QST • Willingness to refrain from pain meds 12 hours prior to QST 	Exclusion (ALL) QST 
 • Current or recent (6 months) use of artificial fingernails or nail enhancements • Neuropathy or loss of feeling in upper or lower extremities

 Willingness to refrain from strenuous exercise that would cause muscle or joint soreness 48 hours prior to QST 	
Inclusion (Healthy) In addition to (ALL) above: n/a	Exclusion (Healthy) In addition to (ALL) above: 
 Diagnosis of a chronic pain syndrome (mild is fine; but less than 3/10 pain score on any body region) Score >3 on FM 2011 survey
Inclusion (FBSS) In addition to (ALL) above: 
 Has chronic low back pain (+/- leg pain) for > 6 months after a lumbar spine surgery Low back pain severity greater than or equal to 4/10 	Exclusion (FBSS) In addition to (ALL) above: 
 Involved in litigation for low back pain or previous low back surgery
Inclusion (LSS) In addition to (ALL) above: 
 Low back pain severity greater than or equal to 4/10 Willingness to participate in longitudinal follow-up questionnaires post-op 	Exclusion (LSS) In addition to (ALL) above: 
 Involved in litigation for low back pain or previous low back surgery History of a previous back surgery LSS is due to spinal cancer-related diagnoses LSS is urgent or emergent

Eligibility (MRI): In addition to eligibility within each group

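### Hypotheses 1b and 2b predict that groups are similar, but the plan offers only tests of difference and no rule for concluding similarity

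*Combined protocol and SAP*

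**What the plan says.** The hypotheses are set out with the aims at the start of the protocol. Under Hypothesis 1b, patients without pain relief after surgery "will appear phenotypically similar to a cross-sectional cohort of established-FBSS patients". Under Hypothesis 2b they "will have augmented QST changes similar to a cross-sectional cohort of established-FBSS patients". Both hypotheses pair the successes with healthy controls in the same way; 1b makes an exception for back pain.

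The analysis is in section II.C. For the failures, phenotypic differences "will be examined using appropriate parametric or non-parametric tests to see if the longitudinally designated AOC-failure cohort is phenotypically similar in nature", with the expectation: "We hypothesize that AOC-failure patients will appear similar to established-FBSS patients". For the successes: "The same comparisons will be explored for the longitudinally designated AOC-success group compared to the cross-sectional healthy controls group". For QST, Aim 2 says: "The same analyses as those conducted for Aim 1 will be used for this aim".

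The comparison groups, from Overall Study Design (II.B), are "50 age and sex-matched healthy controls and 50 age and sex-matched patients with an established diagnosis of FBSS". Healthy controls are excluded for "Score >3 on FM 2011 survey" (II.D.1). The sample-size text in II.C justifies numbers only for the comparison of failure proportions between FM-high and FM-low patients. It gives no power or precision for 1b or 2b.

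**The concern.** A test of difference takes equality as its null hypothesis. Failing to reject it may mean that the groups are alike, or that there were too few patients to see that they are not. The p-value cannot tell these apart. Here the hypothesis of interest is the null itself, and the plan names no other quantity by which it could be judged. Smaller or noisier groups therefore make the predicted finding easier to obtain.

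The outcome-defined failure group is expected to be small, particularly in the half of the surgical cohort that has QST. The protocol intends these results to support a later grant application, so a claim that failures look like established FBSS could carry weight it has not earned.

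A second problem runs the other way. Healthy controls are selected to have low scores on the study's primary measure, while surgical patients have no FM criterion. On FM score, part of any gap between successes and healthy controls comes from eligibility.

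**Working it through.** **1. The plan's own power figure (Analysis 1a).** Inputs from II.C: 50 vs 50, two-sided alpha 0.05, failure proportions 0.10 vs 0.50. With pooled variance under the null:

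- SE under the null = √(0.30 × 0.70 × 2/50) = 0.0917
- SE under the alternative = √((0.10 × 0.90 + 0.50 × 0.50)/50) = 0.0825
- Power = Φ((0.40 − 1.96 × 0.0917)/0.0825) = Φ(2.67) = 0.996, against the stated 0.99

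The alternatives 0.15 vs 0.45 and 0.17 vs 0.43 give 0.918 and 0.820, against the stated 92% and 82%. The 1a figures reproduce for the chi-squared test without continuity correction. They say nothing about 1b or 2b.

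**2. Group sizes for 1b and 2b.** All three scenarios average 30% failure: (0.10 + 0.50)/2 = (0.15 + 0.45)/2 = (0.17 + 0.43)/2 = 0.30. Of 100 surgical patients, about 30 fail and 70 succeed. Of the 50 with QST, about 15 fail and 35 succeed, assuming the same rate. Each group is set against 50. No loss to follow-up is stated, so none is assumed here.

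**3. Chance that a real difference is non-significant.** Two-sample t test, two-sided alpha 0.05 (assumed, since none is stated for 1b/2b), SD = 1. The non-centrality is d/√(1/n1 + 1/n2), and the 95% CI half-width is t(0.975) × √(1/n1 + 1/n2). For 30 vs 50, √(1/30 + 1/50) = 0.231, non-centrality at 0.5 SD = 2.165, half-width = 1.991 × 0.231 = 0.46. For 15 vs 50, the corresponding values are 0.294, 1.698 and 1.998 × 0.294 = 0.59.

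| Comparison | n | Missed, 0.3 SD | Missed, 0.5 SD | Missed, 0.8 SD | 95% CI half-width |
|---|---|---|---|---|---|
| 1b failure vs FBSS | 30 vs 50 | 75% | **43%** | 7% | 0.46 SD |
| 1b success vs healthy | 70 vs 50 | 64% | 24% | 1% | 0.37 SD |
| 2b failure vs FBSS | 15 vs 50 | 83% | **61%** | 24% | 0.59 SD |
| 2b success vs healthy | 35 vs 50 | 73% | 39% | 5% | 0.44 SD |

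**4. Sensitivity, failure comparisons at 0.5 SD.** The Background quotes an FBSS incidence of 10% to 40%. Over that range the miss rate runs from 71% to 36% for 1b (10 to 40 vs 50) and from 82% to 54% for 2b (5 to 20 vs 50). If about 15% of failures were lost (25 and 13 left), it is 48% and 65%.

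**5. What an equivalence rule could deliver.** Two one-sided tests at 0.05 each, true difference zero, 200,000 simulated trials per case; the margins are illustrative.

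| Comparison | Power, ±0.5 SD | Power, ±0.8 SD |
|---|---|---|
| 30 vs 50 | 38% | 93% |
| 70 vs 50 | 70% | 99% |
| 15 vs 50 | 6% | 70% |
| 35 vs 50 | 46% | 95% |

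At ±0.3 SD, power is about 2% or less throughout. The reason at 15 vs 50 is plain: the 90% CI half-width is 1.669 × 0.294 = 0.49 SD, so even an observed difference of zero only just fits inside ±0.5 SD. In return, the chance of wrongly claiming similarity at a true 0.5 SD difference is held to about 5% or less.

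**The case against.** The strongest reply is that the plan never says a p-value above 0.05 means similar. It says differences will be examined and the success comparison explored, and the Outcome section (V.B) describes an observational study that generates data for later work. That stands as far as it goes: a reader might infer that the groups will be declared similar by default, and no such rule is written. But no other rule is written either, and similarity is what the hypotheses assert. Only Aim 3 is labelled exploratory.

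It is also fair that the risk is uneven. The success comparisons are larger, and a 0.8 SD difference would usually be detected except at 15 vs 50. 1b and 2b are also not what the study is powered for.

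Four stronger readings are tempting and are not supported:

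- *Successes must differ from healthy controls on FM score by construction.* Only the controls are truncated. Surgical patients have no FM criterion and some may score low, so the contrast is biased, not settled in advance. The bias also runs against similarity.
- *The controls are matched to the surgical cohort as a whole, and the tests are unadjusted.* II.B describes matched groups for comparison with the outcome groups, and II.C speaks of matching to the patient cohorts. The target is unclear, and adjustment is not mentioned either way. Outcome status is known only at 6 months, so the subsets may not be matched. That is a reason for adjustment, not proof of mismatch.
- *Only 15 FBSS patients have QST.* The schedule legend suggests this, but II.B and the payment section give 50. That inconsistency is a separate matter.
- *The comparison should use 6-month phenotyping.* Outcome is itself defined by 6-month pain, so pain-related measures at that visit would be partly circular. Surgical QST is pre-operative only.

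**Conclusion.** The concern holds in this form: the planned method does not address the stated hypothesis. Following the plan, the only evidence for similarity would be a non-significant difference. That result would occur 43% of the time (1b) and 61% of the time (2b) when failures truly differ from established FBSS by 0.5 SD, against 24% and 39% for successes versus healthy controls. The CI half-widths of 0.46 and 0.59 SD for the two failure comparisons show how little a null result would exclude.

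These figures assume 30% failure, the same rate in the QST half, no dropout, a t test at two-sided 0.05, and 0.5 SD as a benchmark that the documents do not supply. The separate FM-score issue biases one contrast towards a difference; its size cannot be computed from the documents.

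This should be fixed, but it does not threaten the study's main result: the Analysis 1a test and its stated power are sound on this point.

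**What to change.** Change the Analysis 1b text, and through it Aim 2, as follows:

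- For each measure, report the standardised mean difference with a 95% CI from a regression adjusted for age and sex, both already collected.
- State that a non-significant difference will not be read as similarity.
- Either fix and justify a margin for the key measures before outcomes are seen, claim similarity only where the 90% CI lies wholly inside it, and otherwise report inconclusive; or label 1b and 2b descriptive and present estimates with intervals.
- Show FM score for successes versus healthy controls descriptively only, noting the eligibility limit.

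The cost is analysis wording and a few regression models, with no new patients or visits. The downside is that many comparisons will be inconclusive. At an illustrative 0.5 SD margin, equivalence power is about 38% for failures versus FBSS in 1b and 6% in 2b. With the FBSS group held at 50, about 109 failures would be needed for 80% power. Unless a wider margin can be justified, a descriptive label is the realistic choice for 2b.
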